7.1 Pathology

Pathology must be reviewed in the UCSF pathology department

7.1.1 Review of Outside Pathology

If a patient presents with a biopsy from an outside institution of WHO grade 2 glioma, all H&E slides [and ideally unstained slides or a block] and a copy of the pathology report, will be reviewed by the UCSF pathology department to confirm pathology.

If WHO grade 2 glioma pathology is confirmed, the patient is eligible for the study

7.1.2 Laboratory Specimen Collection Procedures

Pathological criteria: 1) At the time of the clinically indicated surgical resection (post-pre-surgical therapy), the resected tumor will be subjected to pathological diagnosis by one of the 2 study neuro-pathologists at UCSF, and and diagnosed as WHO grade II glioma. If the tumor is found to be at higher grade (WHO grade III or IV), the patient will be ineligible for the post-surgery phase of the study, and replaced.

7.1.3 Tumor Tissue Collection

In the operation room, at the time of surgical resection, after adequate tissue is provided to UCSF Medical Center Pathology for diagnosis, the request is made that approximately 0.3 grams of remaining viable tumor tissue is acquired and divided as follows by the Brain Tumor Research Center Tissue Bank.

- 1. 300 mg tumor tissue is snap frozen and collected for banking
- 2. 200 mg tumor tissue will be kept fresh and used for flow cytometric analysis of tumor-infiltrating leukocytes (TILs)

Note: A patient must have at least 200 mg tumor tissue available for TIL to remain eligible for the study.

7.2 Peripheral Blood Samples for Immunologic Monitoring

At the time of clinically indicated surgical resection, peripheral blood samples (8 x 10 cc green top tubes and 1 x 5 cc red top tube) will be collected in the operating room. Samples will be labeled by study identification number and stored at room temperature until transferred to the Cancer Immunotherapy Lab for processing. Immunological assays will be performed by the [name] Lab.

At additional time points (see calendar of events) peripheral blood samples (8 x 10 cc green top tubes and 1 x 5 cc red top tube) will be collected by research staff. Samples will be labeled by study identification number and stored at stored at room temperature until transferred to the Cancer Immunotherapy Lab for processing. Immunological assays will be performed by the [name] Lab.

All assay samples will be de-identified.

7.3 Peripheral Blood Samples for Pharmacokinetics

12 April 2020 Page 59 of 88 confidential

In Arm 1 (with varlilumab) patients, at each of a total of 5 visits with varlilumab infusion (D- 23 ± 2 , A1, A7, A13, and A19), two peripheral blood samples (1 x 10 cc red top tube/draw) will be drawn from the arm contralateral to the infusion site prior to administration and at 30 minutes (\pm 5 minutes) after the end of the varlilumab infusion. An additional sample should be drawn as soon as possible for any patients who experience as infusion reaction. Samples will be stored at room temperature and sent to the Cancer Immunotherapy Lab for processing. Analysis will be performed by the [name] Lab.

7.4 Tissue Bank

All available participants' tumors (including ones obtained by the scheduled surgery in the protocol and ones that may be obtained after the study treatment due to progression) will be banked in the UCSF brain tumor research center (BTRC) tumor bank.

12 April 2020 Page 60 of 88 confidential

8 Correlative/Special Studies

8.1 Immunological Monitoring of PBMCs

Analyses of immune responses in PBMC will allow non-invasive evaluation of vaccine-induced immune response. As one of two co-primary endpoints of the current study, we will determine the response rate and magnitude of CD4+ and CD8+ T-cell responses against the IMA950 peptides in pre- and post-vaccine PBMC using a novel, flow-cytometry-based 2D *ex vivo* assay system. We will determine whether Arm 1 patients demonstrate higher response rate and/or magnitude of response compared with Arm 2 patients.

As the primary method of PBMC analysis, we will use a novel 2D multimer staining-based assays. ⁸³ The use of fluorescently labeled MHC multimers has become an essential technique for analyzing disease- and therapy-induced T-cell immunity. However, limitations on available PBMCs from patients preclude a comprehensive analysis of T-cell immunity. To address this issue, Hadrup et al. developed a combinatorial encoding strategy that allows the parallel detection of a multitude of different T-cell populations in a single sample (2D multimer staining-based assays). ⁸³ Detection of T-cells from PBMC by combinatorial encoding is as efficient as detection with conventionally labeled multimers but results in a substantially increased sensitivity and, most notably, allows comprehensive screens to be performed. We have confirmed that we can detect increases of IMA950-specific T-cells using PBMC samples obtained from GBM patients receiving IMA950 vaccines.

As the primary method to evaluate the relative immune response levels between two Arms, the relative magnitude of responses against each of IMA950 antigens will be compared between two Arms by comparing the sum of post-vaccine tetramer+ percentages of all time points from all patients in each of two Arms.

As an exploratory evaluation, a subject will be considered to be an immunological responder, if at any of two consecutive post-vaccine time points (i.e., Weeks A13, 19 and A25):

- 1. Presence of a CD4+ or CD8+ T cell population which shows positive tetramer staining against any of IMA950 antigens.
- 2. Four-fold increase of the frequency of the tetramer positive cells within the CD4+ or CD8+ T cell population at the considered post-vaccination time points versus the prevaccination time point.

Responders are to be classified based on the number of IMA-950 antigens to which the patient responded (e.g., responders to one antigen, two antigens, and ≥3 antigens). Numbers of these responders will be compared between Arm 1 and Arm 2.

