Post-surgery phase: For All patients, at least two weeks after the post-op steroid is tapered, but within 10 weeks post-surgery, the IMA950/poly-ICLC vaccines will be resumed and repeated every 3 weeks for 8 doses (Weeks A1, A4, A7, A10, A13, A16, A19 and A22; defining Week A1 as the week of the first post-surgery vaccine dose). The vaccines will be injected s.c. in the upper fronto-medial side of right thigh with 48±6 hours post-vaccination phone assessment. Patients will be evaluated for any possible adverse events (AEs), regimen limiting toxicity (RLT), and clinical response during clinic visits. For Arm 1 patients, Varlilumab (CDX-1127) will be administered i.v. on the day of A1, A7, A13 and A19 vaccines following the s.c. vaccination and PK samples (1 x10 cc red top tube/draw) will be collected prior to varlilumab administration and 30 minutes (+ 5 minutes) after the infusion has ended .

Weeks A1, A13, A19 and A25: PBMC samples (80 mL/draw) will be obtained to monitor induction of anti-IMA950 T-cell responses as well as T-cell and myeloid cell subsets by flow-cytometry.

Post-Op (within 4 weeks before Week A1) Weeks A10 and A25: MRI scans

12 April 2020 Page 11 of 88 confidential

Study Objectives:

Primary (two co-primary endpoints):

Safety: We will evaluate the incidence and severity of adverse events associated with the treatment regime, with an early stopping rule based on the frequency of Regimen Limiting Toxicity (RLT).

Immunological activity. We will determine the magnitude of CD4+ and CD8+ T-cell responses against the IMA950 peptides in pre- and post-vaccine PBMC using a novel, flow-cytometry-based 2D *ex vivo* assay system. We will determine whether Arm 1 patients demonstrate significantly higher magnitude of response compared with Arm 2 patients.

Exploratory

- 1. To evaluate IMA950-reactive T-cell infiltration and CXCL9/10 expression in tumors resected from Arm 1 and Arm 2 patients (We will compare these readouts between the two groups in a preliminary manner and the historical control patients who were enrolled in IRB# 15-17078 vaccine study).
- 2. To evaluate IMA950-reactive T-cell receptor (TCR) clonotypes in tumors resected from Arm 1 and Arm 2 patients (We will compare this between the two groups in a preliminary manner (and the historical control patients who were enrolled in IRB# 15-17078 vaccine study).

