4.3 Replacement

Patients who receive at least 4 post-surgery vaccines will not be replaced because their PBMC on week 13 would allow for the primary endpoint evaluation. Subjects who are considered non-evaluable for the immunological endpoint will be replaced but still evaluated for the primary endpoint of safety and the secondary endpoint of efficacy. Evaluable patients for the immunological primary endpoint are study-eligible patients who receive at least four post-surgery vaccines. If the pathological diagnosis upon the resected tissue indicates WHO III or IV grade tumors, those patients will be ineligible for post-surgery courses and replaced.

5 Treatment Plan

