5.5 Treatment Period

5.5.1Study Procedures: Days -23 \pm 2; Days -16 \pm 2; Days -9 \pm 2; Days -2 \pm 2

- Physical/neurological examination
- Vital signs pre-treatment and one hour post-treatment
- Interval medical history
- KPS
- Review of concurrent medications
- Adverse event assessment
- Complete blood count (CBC) with differential and platelet count
- Blood chemistry assessment, including:
 - Alkaline phosphatase, aspartate aminotransferase/alanine aminotransferase (ALT/AST), total bilirubin, calcium, blood urea nitrogen (BUN), creatinine, total protein, albumin, random glucose, potassium, sodium, chloride, bicarbonate
- Vaccination with IMA-950 plus poly-ICLC (one formulation)
- Varlilumab (Arm 1 patients only) on Day -23 ± 2

- Collection of 8 x 10cc green top tubes and 1 x 5cc red top tubes for research blood samples on Day -23 ± 2
- (Arm 1 patients only) on the day of Varlilumab infusion (Day-23 ± 2), PK samples (1 x 10 cc red top tube/draw) should be drawn from the arm contralateral to the infusion site prior to administration and at 30 minutes (±5 minutes) after the end of the varlilumab infusion. An additional sample should be drawn as soon as possible for any patients who experience an infusion reaction.
- Assessment of vaccine injection site 48±6 hours post-injection which can be done
 either by phone or in person. Following Day -2 administration, the follow-up
 assessment will be on the day of surgery. The PI or a clinical co-investigator
 should visit the patient in the ward and make the assessments.

5.5.2Study Procedures, Day 0 (Surgical date)

- Pre-operative MRI per institutional standard of care (with a window of -2 days)
- Intraoperative collection of ≥ 0.5 grams of tumor tissue, snap frozen
- Intraoperative collection of 8 x 10cc green top tubes and 1 x 5cc red top tubes for research blood samples

5.5.3Study Procedure, Post-Op, within 14 ± 2 days of surgery

- Post-operative MRI
- Final pathology confirmation of WHO grade 2 glioma
- Review of expected date off of dexamethasone
- Vital signs
- Interval medical history
- KPS
- Review of concurrent medications
- Adverse event assessment
- Complete blood count (CBC) with differential and platelet count
- Blood chemistry assessment, including:
- Alkaline phosphatase, aspartate aminotransferase/alanine aminotransferase (ALT/AST), total bilirubin, calcium, blood urea nitrogen (BUN), creatinine, total protein, albumin, random glucose, potassium, sodium, chloride, bicarbonate

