12.1 Statistical Analysis Plan

- **12.1.1 Primary Safety Objective:** Evaluate the incidence and severity of adverse events associated with the treatment regime. The proportion of patients experiencing Regimen Limiting Toxicity (RLT, Section 5.3.1) in each arm will be tabulated with 95% exact (Clopper-Pearson) confidence intervals. The proportions of patients experiencing RLT will be compared between arms by the Fisher's exact test. The power of this test is described in Section 12.3. The early stopping rule for RLT is described in Section 12.2.
- **12.1.2 Primary Immunogenicity Objective:** Detection of vaccine-induced immune response in pre- and post-vaccine PBMC. The standardized difference between pre- and post-vaccine PBMC will be compared between arms via a two-sample Student's *t* test. We assume the magnitude of difference will be greater in Arm 1 than Arm 2. If the *t* test assumptions are not met and the data cannot be transformed in such a way that the assumptions are met, a Wilcoxon Rank Sum test will be used. Based on a one-sided two-sample equal variance t-test, the statistical power will be 80% with 15 patients per arm if the difference between arms is at least 0.8 with a standard deviation for both arms of 1.0 with a significance level of 0.10.
- **12.1.3 Exploratory Efficacy Objective:** Evaluation of IMA950-reactive T-cell infiltration and CXCL9/10 expression in tumors resected from Arm 1 and Arm 2 patients. In surgically resected tumor tissues from Arm 1 (IMA950+poly-ICLC and varlilumab) and Arm 2 (IMA950+poly-ICLC alone) patients, we will evaluate numbers of tumor-

12 April 2020 Page 75 of 88 confidential

- infiltrating CD4⁺ T-cells CD8⁺ T-cells (by flow-cytometry) and CXCL10 expression (by RT-PCR). This comparison will be made via two-sample t-tests unless the assumptions are not met then a Wilcoxon alternative will be employed.
- 12.1.4 Exploratory Efficacy Objective: To evaluate IMA950-reactive TCR clonotypes in tumors resected from Arm 1 and Arm 2 patients. Our expectation is to see a higher number of copies of vaccine-specific TCRs (frequency/total tumor DNA) in Arm 1 samples than in Arm 2 samples. This comparison will be made via two-sample t-tests unless the assumptions are not met then a Wilcoxon alternative will be employed.

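### Section 8.1 calls primary a post-vaccine tetramer sum that omits baseline and grows with the number of samples, and nothing reconciles it with the powered t test in Section 12.1.2

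*Combined protocol and SAP*

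**What the plan says.** Two sections each describe the primary immunological comparison between arms.

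- **Section 8.1** introduces its measure with "As the primary method to evaluate the relative immune response levels between two Arms". For each antigen separately, the comparison is made by "comparing the sum of post-vaccine tetramer+ percentages of all time points from all patients in each of two Arms". It names no test, baseline adjustment or error rate.
- **Section 12.1.2** states: "The standardized difference between pre- and post-vaccine PBMC will be compared between arms via a two-sample" Student's t test, with a Wilcoxon rank sum test if the assumptions fail. The power statement belongs to this test: "Based on a one-sided two-sample equal variance t-test, the statistical power will be 80% with 15 patients per arm", for a difference of 0.8, a standard deviation of 1.0 and a significance level of 0.10. It does not name the antigens or how they are combined, the T-cell subset, the post-vaccine time point, or how the difference is standardized.

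The evaluability rule is in Section 4.3: "Evaluable patients for the immunological primary endpoint are study-eligible patients who receive at least four post-surgery vaccines". Such patients are not replaced "because their PBMC on week 13 would allow for the primary endpoint evaluation".

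The set of post-vaccine samples varies by place. The Synopsis (post-surgery phase) says "Weeks A1, A13, A19 and A25: PBMC samples (80 mL/draw) will be obtained to monitor induction of anti-IMA950 T-cell responses". Section 5.5.2 adds a draw at surgery: "Intraoperative collection of 8 x 10cc green top tubes and 1 x 5cc red top tubes for" research samples. The responder rule in Section 8.1 uses A13, A19 and A25 only.

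The status of response rate also varies. Sections 1.1.2, 2.8 and 9.1.2 and the opening of 8.1 put it in the co-primary objective. Section 8.1 later calls responder status exploratory, and the Synopsis objective names magnitude only.

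**The concern.** A statistician who follows Section 8.1 and one who follows Section 12.1.2 would analyse different variables, and both could say they had followed the plan's primary analysis. This is more than missing detail, because the measure in 8.1 is unsuitable as stated. It takes no account of a patient's pre-vaccine level, although the objective concerns response from pre- to post-vaccine blood. It is also a sum that is not divided by the number of samples, so an arm with fewer late draws shows a smaller value even when the treatment makes no difference.

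The protocol's own rules allow late draws to be lost. A regimen limiting toxicity takes a patient off study (5.6.1), progression ends treatment (5.10), and the post-vaccine follow-up lists no research blood (5.5.8 and the Section 6 calendar). A patient can therefore be evaluable and still lack A19 and A25.

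The trial is open label (4.1). If the choice between the two measures is left until results can be seen by arm, the one-sided 0.10 error rate no longer describes the comparison that is reported.

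**Working it through.** **1. The plan's own figure.** Inputs from 12.1.2: n = 15 per arm, difference 0.8, SD 1.0, one-sided alpha 0.10. The noncentrality is 0.8 / (1.0 × √(2/15)) = 2.19 with 28 degrees of freedom. The noncentral t distribution gives power 0.810. The normal approximation gives 0.818 and a required n of 15 per arm. The stated 80% is reproduced, for the 12.1.2 variable only.

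**2. Model for the sum.** Take A13, A19 and A25 as the post-vaccine samples. Every patient has A13, m of 15 patients in one arm lack A19 and A25, and the other arm is complete. There is no arm effect. Let r be the mean level at A19 and A25 relative to A13. The documents give neither m nor r; both are assumed.

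Ratio of arm totals = [15 + 2r(15 − m)] / [15(1 + 2r)]

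- m = 3, r = 1: (15 + 24) / 45 = 39/45 = 0.867.
- m = 1 to 5, r = 1: 43/45 = 0.956 down to 35/45 = 0.778.
- Extremes for m = 1 to 5 and r = 0.25 to 4: 22/22.5 = 0.978 and 95/135 = 0.704.
- With five draws counted (surgery, A1, A13, A19, A25), equal levels and m = 3: 69/75 = 0.92.

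With 3 incomplete patients and r = 1, that arm needs per-sample levels 1/0.867 = 1.154 times the other arm's, or 15% higher, just to tie. The range is 7% (r = 0.25) to 22% (r = 4).

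**3. Does the reading of the sum matter?** If the sum is formed within each patient and then averaged over 15 patients, both arm totals are divided by 15, so the ratios in step 2 do not change. Only the effect of arm size differs. A 16 to 14 split moves a literal arm total by 16/14 = 1.14 with no treatment effect, whereas a mean of per-patient sums is unaffected.

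**4. Which replacement is robust?** Same model, m = 3, before baseline subtraction. For the mean over a patient's available samples, let c = (1 + 2r)/3; the ratio of arm means is (12c + 3)/(15c).

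| r | Sum | Mean of available samples | A13 only |
|---|---|---|---|
| 0.25 | 0.933 | 1.200 | 1.000 |
| 0.5 | 0.900 | 1.100 | 1.000 |
| 1 | 0.867 | 1.000 | 1.000 |
| 4 | 0.822 | 0.867 | 1.000 |

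The mean of available samples is off by 20% at r = 0.25, where the sum is off by 6.7%. The two errors are equal in size at r = 0.5, and the mean is better only above that. A13 alone does not shift, but only because the model gives every patient an A13 sample.

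**5. Is an A13 sample assured?** No. The fourth post-surgery vaccine is at A10, and the A13 draw falls at the visit for the fifth (5.5.5 and the Section 6 calendar). A patient who stops after the fourth dose is evaluable under 4.3 but may have no A13 sample.

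**The case against.** The best defence is that Section 12.1.2 plainly governs. It sits under the Statistical Analysis Plan heading and gives the test, fallback, sidedness, alpha and sample size, while 8.1 sits among the correlative studies and may only describe the readout loosely. Section 4.3 treats the week 13 sample as enough for the primary endpoint, which fits a per-patient pre/post difference and not a sum needing every time point. Much of this stands, and it is why the fix keeps 12.1.2. It does not remove the conflict: 8.1 uses the word primary, separately labels the responder analysis exploratory, and is nowhere subordinated to 12.1.2.

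Three stronger readings are tempting and are not supported.

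- A reader might infer that the 8.1 measure has no between-patient variance and so cannot be tested. The sentence can also be read as a sum within each patient, compared across patients, and a t test could then be run. Omission of baseline and dependence on sample count remain on either reading.
- A reader might infer that the variable in 12.1.2 is wholly undefined. It does describe a between-arm measure, 4.3 points to week 13, and the Synopsis places the pre-vaccine draw at day -23. What stays open is the antigen combination, the T-cell subset, the standardization and an explicit statement of the time point.
- A reader might infer an expected bias against one arm. The documents give no loss rates. Equal loss with equal profiles gives a ratio of 1.00.

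**Conclusion.** The point holds. Section 8.1 states a primary between-arm method that differs from the powered analysis in 12.1.2, omits the pre-vaccine value, and depends on how many samples each patient gives. Nothing reconciles the two sections. This is a rule that is wrong as written, not merely an omission.

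The figure of 87% of the other arm's total shows sensitivity; it is not a forecast. It assumes 3 of 15 patients with A13 only, in one arm, with equal levels over time and no arm effect. The full assumed range is 98% to 70%. The power statement is sound (0.81 against 80% stated) but applies only to the 12.1.2 test. The inconsistent status of response rate is a further conflict within the same co-primary endpoint and belongs in the same correction.

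**What to change.** - State that 12.1.2 governs, and remove the primary label from the sum in 8.1.
- Define one value per patient as the change from day -23 to A13, the sample on which 4.3 relies. Name the antigen combination, the T-cell subset and the standardization. Run one between-arm test at one-sided 0.10, keeping the Wilcoxon fallback.
- State how an evaluable patient without an A13 sample is handled.
- Report the mean over available post-vaccine samples minus the day -23 value as a sensitivity analysis only, because it can shift when late samples are missing and levels change after A13.
- Label per-antigen comparisons secondary or descriptive.
- Give response rate the same status in the Synopsis and in Sections 1.1.2, 2.8, 8.1 and 9.1.2.
- Lock the definition before assay results are reviewed by arm, since the trial is open label.

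The cost is protocol and SAP wording, with no new samples, assays or patients; the planned 15 per arm and its power carry over to the 12.1.2 test. The downside is that per-antigen results lose primary status and samples after A13 do not enter the primary test.

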8.2 Enzyme Linked Immuno-SPOT (ELISPOT) Assays

12 April 2020 Page 61 of 88 confidential

Frequencies of T-lymphocytes reactive to the IMA950+poly-ICLC vaccine in PBMC prior to and after the treatment can be measured by ELISPOT assay. The ELISPOT assays will be done at the same time point at least for one individual participant to avoid inter-assay variability. We will use IFN- γ ELISPOT as the readout to assess Type-1 T-cell response.

The detailed Standard Operation Procedures are available in [name] Lab. A subject will be considered to have responded, if at any of two consecutive post-vaccine time points, the number of spots is double that at baseline, and there are at least 10 spots/20,000 cells, and if the number of the post-vaccine spots is at least three times the standard-deviation of the pre-treatment value. This definition provides some protection against false positive response.

